### 3.2 Patient Eligibility Criteria

#### **INCLUSION CRITERIA**

#### 3.2.1 Age

Patients must be ≥365 days and <23 years of age at the time of enrollment.

#### 3.2.2 Diagnosis

Patients with any malignancy who will receive HDMTX given as a 5 g/m2 infusion over 24 hours and a history of ≥1 of the following:

- Documented decreased renal function, as defined as Creatinine greater than 1.5 x baseline or GFR <65ml/min/1.73m^2.
- History of prior nephrotoxicity with HDMTX as evidence by increased creatinine to 1.5 x baseline or need for dialysis or carboxypeptidase
- History of Grade 3 adverse event (AE) related to HDMTX (mucositis, myelosuppression, nephrotoxicity, hepatotoxicity) based on the NIH Common Terminology Criteria for Adverse Events (CTCAE) version 4.0
- Provider concern patient is at risk for MTX toxicity, such as a prior history of treatment with nephrotoxic chemotherapy, history of HDMTX-related neurotoxicity, or antimicrobial/antifungal therapy

Protocol Version 8.0 Date: June 17, 2015

#### **EXCLUSION CRITERIA**

- 3.2.3 Unable to draw labs for HDMTX serum concentration
- 3.2.4 Enrollment on a protocol (COG or other) which restricts proposed dose modifications
- 3.2.5 Patients with Trisomy 21
- 3.2.6 Patients with > grade 1 neurologic toxicity at the time of enrollment that is attributed to unresolved prior methotrexate toxicity
- 3.2.7 Patients with ≥ grade 3 chronic kidney disease at enrollment (eGFR or CrCl < 30ml/min/1.73m²)

#### REGULATORY

- 3.2.8 Informed consent for participation in this study must be obtained within 30 days from the start of HDMTX on this protocol and prior to any research procedures from the patient and/or the patient's legally authorized guardian in accordance with institutional policies approved by the U.S. Department of Health and Human Services
- 3.2.9 All institutional, FDA, and NCI requirements for human studies must be met.

#### 4. TREATMENT PLAN

#### 4.1 Overview of Treatment Plan

Our prospective study will enroll patients who will receive HDMTX given as a 5g/m² 24-hour infusion. Enrolled patients will be receiving HDMTX as determined by their primary provider. Patients are eligible to be enrolled at any time point during their treatment course, and may participate during any one or more of their multiple HDMTX administrations.

### **Concomitant Medication Restrictions:**

- 1. Sulfamethoxazole and Trimethoprim (SMX-TPM); synonyms: Bactrim, Co-trimoxazole
- 2. Non-steroidal anti-inflammatory medications (NSAIDS)
- 3. Penicillins
- 4. Proton pump inhibitors
- 5. Aspirin-containing medications

Hold the above medications on the day of HDMTX infusion and for at least 72 hours after the start of the HDMTX infusion and until the MTX level is less than 0.4µM (In the presence of delayed clearance continue to hold these medications until MTX level is less than 0.1 µM):

As per the Children's Oncology Group (COG) and institutional guidelines, restricted medications should be stopped (i.e. 1. Sulfamethoxazole and Trimethoprim (SMX-TPM); synonyms: Bactrim, Cotrimoxazole; 2. Non-steroidal anti-inflammatory medications (NSAIDS); 3. Penicillins; 4. Proton pump inhibitors; 5. Aspirin-containing medications), and prior to receiving HDMTX patients will receive IV hydration with D5  $\frac{1}{4}$  NS with NaHCO $_3$  3 mEq/100 mL at 200 mL/m $^2$ /hr for a minimum of 2 hours, until urine pH  $\geq$  7.0 and  $\leq$  8.0 and urine specific gravity  $\leq$ 1.010.

Once these parameters are met, between hours 0-1 of the protocol patients will receive methotrexate 500 mg/m² in D5  $\frac{1}{4}$  NS with NaHCO3 3 mEq/100 mL at 200 mL/ m² IV over 60 minutes. This will be followed immediately by Hours 1 to 24 Methotrexate 4500 mg/m² in D5  $\frac{1}{4}$  NS with NaHCO3 3 mEq/100 mL 4600 mL/ m² IV at 200 mL/m²/hr for 23 hours.

Dose adjustments will be made based on the following tables. Adjustments should be made as soon as possible after MTX levels checked are resulted. Interventions are expected to be done within 120 minutes of sending the MTX level.

### A. Interventions at 2 hours

If MTX level	<100µM	≥100µM
is:		
MTX	·Continue unchanged	·Stop infusion for 1 hour
administration	_	At restart time; restart MTX at 50% reduction
intervention		from original infusion rate; therefore, restart
		at 100 mL/m²/hr
Fluid	·Continue unchanged	·At restart time; begin D5 ¼ NS with
intervention	_	NaHCO3 3 mEq/100 mL at 100 mL/m  /hr)
MTX level	·Check 6 hour MTX level and again at	·Check 8 hour MTX level and then per the
specific lab	24, 36, 42 and 48 hours per COG	COG algorithm# at 24, 36, 42 and 48 hours*
instructions	algorithm#	

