### B. Interventions at 6 hours (\*8 hours if 2 hour level was ≥100µM)

If MTX level is:	<75μM	≥75µM/<100µM	≥100µM
MTX administration intervention	·Continue Unchanged	·Reduce MTX infusion 20% from MOST RECENT infusion rate; Therefore, if (select A OR B): A) 2 hr MTX level was <100 μM and therefore, infusion rate was 200 mL/m²/hr then restart at 160 mL/m²/hr B) 2 hr MTX level was ≥100 μM and therefore, infusion rate was 100 mL/m²/hr then restart at 80 mL/m²/hr	·Stop infusion for 1 hour ·At restart time; restart MTX at 50% reduction from MOST RECENT infusion rate; Therefore, if (select A OR B): A) 2 hr MTX level was <100 µM and therefore, infusion rate was 200 mL/m²/hr then restart at 100 mL/m2/hr B) 2 hr MTX level was ≥100 µM and therefore, infusion rate was 100 mL/m²/hr then restart at 50 mL/m²/hr
Fluid intervention	·Continue unchanged	Select A OR B: A) If 2 hr MTX level was <100 µM and therefore, there was no previous additional fluid order then begin D5 ¼ NS with NaHCO3 3 mEq/100 mL at 40 mL/m²/hr B) If 2 hr MTX level was ≥100 µM and therefore, additional D5 ¼ NS with NaHCO3 3 mEq/100 mL was already running at 63.5 mL/m²/hr then increase this fluid to run at 120 mL/m²/hr	Select A OR B A) If 2 hr MTX level was <100 µM and therefore, there was no previous additional fluid order then begin D5 ¼ NS with NaHCO3 3 mEq/100 mL at 100 mL/m²/hr B) If 2 hr MTX level was ≥100 µM and therefore, additional D5 ¼ NS with NaHCO3 3 mEq/100 mL was already running at 100 mL/m²/hr then increase this fluid to run at 150 mL/m²/hr

MTX level	·Check MTX level	·Check MTX level again at 24,	·Check MTX level again at 24,
specific lab	again at 24, 36, 42	36, 42 and 48 hours per COG	36, 42 and 48 hours per COG
instructions	and 48 hours per	algorithm#	algorithm#
	COG algorithm#		_

\*see COG algorithm on page 21

Subjects will come off protocol therapy for infusion delays longer than 2 hours. In addition, the total methotrexate infusion time, on this study, should be no longer than 26 hours. Infusions should only be extended past 24 hours to accommodate stops for other med infusions. Increases in rate of MTX infusion to ensure completion within this time frame are **not** allowed.

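### Table A ties replacement fluid to the restart, so no hydration or bicarbonate is ordered for the 1-hour methotrexate stop after a 2-hour level of 100 µM or more

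*Combined protocol and SAP*

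**What the plan says.** Section 4.1 orders separate IV hydration only before methotrexate: D5 ¼ NS with NaHCO3 3 mEq/100 mL at 200 mL/m²/hr "for a minimum of 2 hours, until urine pH" is between 7.0 and 8.0 and specific gravity is at most 1.010. From hour 0 the ordered fluid is the drug diluent, with the same bicarbonate content: 200 mL/m² over the first hour, then "4600 mL/ m² IV at 200 mL/m²/hr for 23 hours".

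In table A (interventions at 2 hours), column ≥100 µM:
- The methotrexate cell says "Stop infusion for 1 hour", then restart at 100 mL/m²/hr.
- The fluid cell says "At restart time; begin D5 ¼ NS with" bicarbonate at 100 mL/m²/hr.

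In table B (6 hours, or 8 hours after a high 2-hour level), column ≥100 µM, the bag is again stopped for 1 hour. The fluid cell has two options and names no start time:
- Option A, for a 2-hour level below 100 µM: "there was no previous additional fluid order then begin D5 ¼ NS with NaHCO3 3 mEq/100 mL at 100 mL/m²/hr".
- Option B, for a 2-hour level of 100 µM or more: fluid "already running at 100 mL/m²/hr then increase this fluid to run at 150 mL/m²/hr".

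Two general sentences in section 4.1 govern timing: "Adjustments should be made as soon as possible after MTX levels checked are resulted" and "Interventions are expected to be done within 120 minutes of sending the MTX level".

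**The concern.** The methotrexate bag is also the hydration bag, so stopping the drug stops the fluid unless something else is ordered. Table A does order something else, but sets its start at the end of the stop. Followed exactly, the ordered total runs 200, then 0, then 200 mL/m²/hr.

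This sits badly with the protocol's own reasoning. Section 2.3 relies on hyper-hydration and urine alkalinization during the infusion to promote clearance, and section 2.3.4 names both as concurrent protection against nephrotoxicity. Section 2.3.1 notes that the main metabolites are much less soluble in acid. Patients enter because of reduced renal function, earlier methotrexate toxicity or provider concern about it (section 3.2.2), and the stop is the response to a high level. Pausing the drug does not remove the methotrexate already given.

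**Working it through.** **Planned fluid, reproduced.** 23 h × 200 mL/m²/hr = 4600 mL/m², as stated in section 4.1. Adding the first hour, 4600 + 200 = 4800 mL/m² over 24 hours. At 3 mEq/100 mL, 4800 × 3/100 = 144 mEq/m² of NaHCO3, or 6 mEq/m² per hour.

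**Ordered totals once the infusion is running again** (mL/m²/hr, from tables A and B):

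| Branch | Methotrexate bag | Added fluid | Total |
|---|---|---|---|
| Table A, ≥100 µM | 100 | 100 | 200 |
| Table B, 75 to <100 µM, option A | 160 | 40 | 200 |
| Table B, 75 to <100 µM, option B | 80 | 120 | 200 |
| Table B, ≥100 µM, option A | 100 | 100 | 200 |
| Table B, ≥100 µM, option B | 50 | 150 | 200 |

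Every pair restores 200. (One table B cell describes the earlier added fluid as running at 63.5 mL/m²/hr. That is a separate mismatch and does not change the pairs above.)

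**Table A stop hour.** Bag 0 + added fluid 0 = 0 mL/m²/hr ordered. Table B's option A confirms that no additional fluid is running before a 2-hour intervention.
- Shortfall: 200 − 0 = 200 mL/m², and 200 × 3/100 = 6 mEq/m² of NaHCO3.
- Share of 24 hours: 200/4800 = 4.2% (6/144 = 4.2%).
- Share of the fluid planned to the 8-hour draw: 200/(8 × 200) = 12.5%.

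**Table B stop hour.** The fluid cell is undated, so each option has a range. The upper rate applies if the new fluid starts at the stop; the lower applies if the cell gives restart rates.
- Option A: 0 to 100 mL/m²/hr ordered; shortfall 100 to 200 mL/m² (3 to 6 mEq/m²).
- Option B: 100 to 150 mL/m²/hr ordered; shortfall 50 to 100 mL/m² (1.5 to 3 mEq/m²).
- Stops at both 2 and 8 hours (table A, then option B): 200 + 50 = 250 to 200 + 100 = 300 mL/m²; 250/4800 = 5.2% to 300/4800 = 6.25%. NaHCO3: 7.5 to 9 mEq/m².

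**Setting of the table A gap.** With the level sent at hour 2 and up to 120 minutes to act, the stop begins at hours 2 to 4 and restart falls at hours 3 to 5.
- Methotrexate already given: 500 + 1 × 4500/23 = 696 mg/m² at hour 2, up to 500 + 3 × 4500/23 = 1087 mg/m² at hour 4.
- Fluid already given: at least 2 × 200 + 2 × 200 = 800 mL/m², including pre-hydration.
- Time back at 200 mL/m²/hr before the 8-hour draw: 3 to 5 hours.

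**The case against.** The strongest reply is that nothing tells staff to withhold fluid. The zero is only a missing order, and section 4.1 introduces its fluid orders as following COG and institutional guidelines that are not reproduced. Sections 2.3 and 2.3.4 present hydration as standard during treatment, and the constant total of 200 signals the intent. The protocol also tolerates other pauses, such as stops for other medicines, without giving a fluid rate. This stands as a limit: what happens at the bedside cannot be judged from the documents. It does not dispose of the point, because table A is not merely silent. It states when the fluid begins, and a specific start time is not naturally overridden by the general sentence about acting as soon as possible.

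The second reply is that the gap is trivial: one hour, after pre-hydration to a urine target, with methotrexate off and fluid soon restored. That also stands, and it keeps the point small.

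The third is that 200 mL/m²/hr during a stop is a clinical choice the documents do not make. That is right, and the rate should be confirmed by the clinical team.

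**Conclusion.** The point holds as a minor safety correction. As written, table A leaves its 1-hour stop without any ordered hydration or bicarbonate: 200 mL/m² and 6 mEq/m² short, 4.2% of the 24-hour plan. This assumes the table is followed literally and that no outside guideline supplies fluid.

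Four stronger readings are not supported:
- A reader might infer that the protocol instructs staff to give no fluid. It does not; the order is absent.
- A reader might infer that the gap is confined to table A, or that it certainly recurs in table B. The undated table B cell allows either reading, so only the ranges above can be given.
- A reader might set table A against the suggested post-infusion guideline, which raises hydration to 200 mL/m²/hr for a 36-hour level above 3 µM. That concerns an optional level about 12 hours after the infusion ends and says nothing about a pause early in the infusion.
- A reader might infer harm to patients or an effect on the 24-hour level. The documents give no means of quantifying a clinical effect, and no effect on the primary endpoint is claimed.

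**What to change.** Reword the table A fluid cell for ≥100 µM along these lines: when the infusion is stopped, begin D5 ¼ NS with NaHCO3 3 mEq/100 mL at 200 mL/m²/hr; at restart, reduce to 100 mL/m²/hr. The clinical team confirms the rate; 200 keeps the total that the protocol orders before the stop and after restart.

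State the same start-at-stop rule in table B's ≥100 µM column, with added fluid at 200 mL/m²/hr during the stop and then 100 (option A) or 150 (option B) mL/m²/hr at restart. This closes the table A gap and settles the undated table B cell.

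The cost is a wording amendment to one cell, one matching sentence, and an update to any order sets built on the tables. It adds no patients, visits, tests or data items.

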### B. Interventions at 6 hours (\*8 hours if 2 hour level was ≥100µM)

If MTX level is:	<75μM	≥75µM/<100µM	≥100µM
MTX administration intervention	·Continue Unchanged	·Reduce MTX infusion 20% from MOST RECENT infusion rate; Therefore, if (select A OR B): A) 2 hr MTX level was <100 μM and therefore, infusion rate was 200 mL/m²/hr then restart at 160 mL/m²/hr B) 2 hr MTX level was ≥100 μM and therefore, infusion rate was 100 mL/m²/hr then restart at 80 mL/m²/hr	·Stop infusion for 1 hour ·At restart time; restart MTX at 50% reduction from MOST RECENT infusion rate; Therefore, if (select A OR B): A) 2 hr MTX level was <100 µM and therefore, infusion rate was 200 mL/m²/hr then restart at 100 mL/m2/hr B) 2 hr MTX level was ≥100 µM and therefore, infusion rate was 100 mL/m²/hr then restart at 50 mL/m²/hr
Fluid intervention	·Continue unchanged	Select A OR B: A) If 2 hr MTX level was <100 µM and therefore, there was no previous additional fluid order then begin D5 ¼ NS with NaHCO3 3 mEq/100 mL at 40 mL/m²/hr B) If 2 hr MTX level was ≥100 µM and therefore, additional D5 ¼ NS with NaHCO3 3 mEq/100 mL was already running at 63.5 mL/m²/hr then increase this fluid to run at 120 mL/m²/hr	Select A OR B A) If 2 hr MTX level was <100 µM and therefore, there was no previous additional fluid order then begin D5 ¼ NS with NaHCO3 3 mEq/100 mL at 100 mL/m²/hr B) If 2 hr MTX level was ≥100 µM and therefore, additional D5 ¼ NS with NaHCO3 3 mEq/100 mL was already running at 100 mL/m²/hr then increase this fluid to run at 150 mL/m²/hr

MTX level	·Check MTX level	·Check MTX level again at 24,	·Check MTX level again at 24,
specific lab	again at 24, 36, 42	36, 42 and 48 hours per COG	36, 42 and 48 hours per COG
instructions	and 48 hours per	algorithm#	algorithm#
	COG algorithm#		_

\*see COG algorithm on page 21

Subjects will come off protocol therapy for infusion delays longer than 2 hours. In addition, the total methotrexate infusion time, on this study, should be no longer than 26 hours. Infusions should only be extended past 24 hours to accommodate stops for other med infusions. Increases in rate of MTX infusion to ensure completion within this time frame are **not** allowed.

The interventions in this protocol occur at the 2 and 6 hour (or 8 hour if the 2 hour level was  $\geq 100 \mu M$ ) time points. After the 24hr HDMTX infusion is complete, the individualized protocol will end and patients will remain on study but be off of the protocol therapy. After this time, management of MTX levels will continue according the treating physician's discretion using standard supportive care guidelines. This is elaborated below in Appendix B, suggested supportive care guidelines based on the COG algorithm. Interventions for toxicity are at the discretion of the treating provider as patients will be off treatment protocol at the 24hr time point. Glucarpidase should be administered based on the treating physician's discretion, with the recommendation that it be administered prior to the development of grade 4 nephrotoxicity and prior to 96 hours after the start of the HDMTX infusion. Administration of CPDG2 after these time points have been shown to be statistically associated with the development of  $\geq$  grade 4 toxicity.

Patients may be re-enrolled on this protocol therapy again for subsequent HDMTX infusions without the need for re-consent. In order to re-enroll, call the study coordinating center as outlined in Section 3.1 PRIOR to the cycle in which the dose modification protocol will be implemented.

The active length of study participation for each patient is 4 weeks after the last high-dose methotrexate infusion or until the next cycle of chemotherapy begins (which ever occurs first). Therefore, the maximum amount of active time on study would be 2.5 months. This would include 4 doses of HDMTX given every other week plus a 4 week follow-up period to assess for side effects.

### 4.2 Study Endpoints

After the initial monitoring of MTX levels and creatinine during the MTX infusion, patients will be followed for the development of HDMTX related toxicity for 4 weeks after their infusion or until their next cycle of chemotherapy begins, whichever is shorter.

#### 5. EVALUATIONS/MATERIAL AND DATA TO BE ACCESSIONED

### At Study Entry

### 5.1 Physical Exam

### 5.2 Laboratory Tests Prior to Treatment

- A maximum of 28 days prior to the first dose of HDMTX on this protocol a nuclear medicine GFR must be performed.
- A maximum of 7 days prior to the first dose of HDMTX on this protocol the following labs will be collected (Week 0 labs): CBC, Chem 10, AST, ALT, total and direct bilirubin, and 10 mL in a purple top (minimum of 5mL will be accepted) of additional blood for MTX transportation genetic analysis. Sample for MTX transportation genetic analysis is optional.

### 5.3 Demographic information

Age, race, leukemia type, cytogenetics of leukemia, leukemia risk stratification, disease status, protocol treated according to, concomitant medication, reason for enrollment on protocol and type of adverse event with prior HDMTX.

### 5.4 Laboratory Tests During Treatment

- Methotrexate levels and creatinine at times 2, 6 (or 8) and 24 hours are required for research purposes. Additional methotrexate levels and creatinine should be performed per institutional standards. Methotrexate levels and creatinine at hours 36 (if methotrexate levels are ≥150 micromolar), 42, 48 and every 6-12 hours thereafter until methotrexate is considered cleared (e.g. ≤0.4 micromolar at hour 48 and/or <0.1 micromolar thereafter) is highly recommended but considered optional. An example of routine post-methotrexate monitoring is outlined in Appendix B.

- The following labs should be drawn at Week 1 and Week 2 and repeated weekly until
  either the next dose of HDMTX is administered or 4 weeks have passed since the last
  dose of HDMTX: CBC, Creatinine, BUN, AST, ALT, total and direct bilirubin.

#### 5.5.2 DNA Extraction and Distribution

Five to 10 mL of peripheral blood will be collected for genotyping purposes prior to the initiation of the methotrexate infusion, during the gathering of additional baseline laboratories. At this time additional baseline labs are routinely collected and peripheral blood mononuclear cells will be optimally present prior to methotrexate/chemotherapy induced myelosuppression. Mononuclear cells will be separated from whole blood using Ficoll-Hypaque centrifugation. DNA will be isolated from the enriched mononuclear cells using the QIAgen DNeasy kit per the manufacturer's instructions. To avoid DNA loss or degradation DNA samples will be stored in Axygen or comparable tubes. Based on prior experience with ALL samples, we expect an average of 18.5mcg of DNA per sample. Most current genotyping techniques require 5-20ng per assay.

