### 1.2 Secondary Aims

- 1.2.1 To determine the incidence of the following side effects in high risk patients receiving high dose methotrexate as a 24 hour infusion: nephrotoxicity, neurotoxicity, mucositis, hepatotoxicity, and myelosuppression.
- 1.2.2 To describe host polymorphisms that may identify risk of methotrexate toxicity or success of this institutional protocol.
- 1.2.3 To describe predictors of successfully achieving an optimum concentration of methotrexate at the end of a 24 hour infusion of HDMTX in patients at high risk of drug toxicity treated with this individualized high dose methotrexate protocol.

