#### 2. BACKGROUND

Methotrexate is a crucial chemotherapeutic agent used to treat children with acute lymphoblastic leukemia (ALL), and is a staple of treatment regimens both nationally and internationally¹. In fact, cure rates for ALL approach 80%, in part due to the incorporation of methotrexate into treatment protocols¹. While all serum concentrations of methotrexate have shown to be efficacious in ALL therapy, when doses above 1g/m² – considered high dose methotrexate (HDMTX) – are given, several leukemic cell methotrexate resistance mechanisms are readily overcome². Most current protocols using HDMTX, including those run by the Children's Oncology Group (COG) now utilize 5g/m² given as a 24 hour infusion in non-Down syndrome leukemia patients³. Many studies have demonstrated the clinical benefits of HDMTX⁴;⁵, even when directly compared to lower doses of methotrexate⁶. Recent data from the National Cancer Institute (NCI) sponsored COG trial AALL0232 compared the effectiveness of HDMTX and 6-MP against Capizzi escalating methotrexate plus PEG asparaginase (C-MTX/ASNase) in patients less than 30 years old with high-risk ALL (HR-ALL). Initial analysis showed that patients randomized to receive HDMTX had significantly higher 5-year event-free survival (EFS) compared to patients who received C-MTX/ASNase (82+ 3.4% versus 75.4 + 3.6%, p=0.006)². This finding lead to all patients with HR-ALL being treated with HDMTX.

However, treatment with HDMTX can be associated with significant toxicity. The risk of morbidity and mortality from methotrexate toxicity increases when the drug is given at high dose. Toxicities are directly correlated with increased drug exposure and since methotrexate is cleared renally, patients with kidney dysfunction are at particularly high risk of complications. In patients treated with HDMTX, 1.8% will experience renal dysfunction. Patients with relapsed ALL are at increased risk of methotrexate toxicity due to prior exposure to nephrotoxic chemotherapy, as are patients with renal injury. Per current COG protocols, patients with certain features indicating a high risk of toxicity to methotrexate will either have their methotrexate arbitrarily reduced by 25%, or it will be omitted from their treatment regimen entirely reducing or eliminating the important anti-leukemic effects of the drug.

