In addition, despite the fact that MTX pharmacokinetics, tumor response and patient toxicities are known to vary greatly and it is known that several germline polymorphisms play a role in this variation, much controversy about the functional consequences of these polymorphisms still exists. Our study, will, by definition, isolate a population of patients with a known increased propensity for certain MTX toxicities. Because the general population minor allele frequency (MAF) is known for many of the polymorphisms known to affect MTX metabolism, this study will provide a unique opportunity to compare rates of certain of these polymorphisms in our study population to that of the general population. This may help elucidate which polymorphisms truly correlate to deficiencies in MTX metabolism. In addition, we may be able to discover which polymorphisms describe a population best suited for individualized MTX dosing.

Though many genetic targets in the folate cycle and intracellular MTX transportation have already been identified, new target genes continue to be discovered. Given that the knowledge base in this field is rapidly expanding, the decision of which polymorphisms to be tested will be determined at the time of analysis, when the study accrual has been met. Common SNPs currently thought to be involved in methotrexate metabolism, pharmacodynamics and toxicity are listed below:

Polymorphism	SNP effect	Approximate MAF (%)	Clinical effect	Reference
MTHFR 677C>T	Reduced activity	15-25	Both increased and decreased risk of myelosuppression reported	37;38
SLC19A1 80G>A	Reduced activity	30-50	Increased hepatotoxicity	39
MTHFR 1298A>C	Reduced activity	15-20	Decreased myelosuppression	40
TYMS 28-bp triple repeat	Increased transcription	40-50	None reported	41

This research does not qualify for an IND as the use of HDMTX is per standard of care treatment of ALL, and the route of administration or dosage level does not significantly increase risk to the patient.

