### **APPENDIX A**

Schedule of Assessments											
			Hours after methotrexate infusion Weeks starts (Week 0)								
Procedures	s	0	2	6 ¹	24	36‡	42‡	482‡	1	2 	Protocol section
Blood for SNP analysis		Х									5.5.2
Nuclear eGFR	Х										5.2
CBC with diff and platelets		Х							Х	Х	5.2
BUN		Х							Х	Х	5.2
AST/ALT/T&D* bilirubin		Х							Х	Х	5.2, 5.4
Creatinine		Х	Х	Х	Х	Х	Х	Х	Х	Х	5.4
Methotrexate level			Х	Х	Х	Х	Х	Х			4.1

S: Screening; Week 0: Week of high dose methotrexate administration; Hour 6 or 8 depending on 2 hour methotrexate level (Sec 4.1); ‡ highly recommended but optional; should be done per institutional standards of post-methotrexate monitoring;  Continue 48 hour labs per algorithm (recommended but optional) (See appendix B);  Repeat Week 2 labs weekly until the next dose of methotrexate or 30 days since last dose of methotrexate; \*T&D: Total and Direct

++ If the level is high at hour 36 or 42, but then the patient "catches up" and the level falls to the expected values of ≤1.0 and/or ≤ 0.4 μM at hours 42 and 48, respectively, resume standard leucovorin and hydration as long as urine output remains satisfactory.

Suggested post HDMTX infusion guidelines based on standard COG guidelines.

36 hr MTX level (if needed) +	42 hr MTX level	48 hr MTX level	Hydration and leucovorin rescue
>3 µM			Increase hydration to 200 mL/m²/hr
>10 µM			
 
Increase hydration to 200 mL/m²/hr.
 
Consider glucarpidase
 

	≤1.0 µM	≤ 0.4 µM	No further leucovorin after Hr 54, no further MTX levels after Hr 48
	1.01-9.9 µM	0.41-5.9 μM	Continue leucovorin at 15 mg/m² q 6 hours after Hr 54 until plasma MTX is < 0.1 μM
	40.40.0.14	0.00.11	Repeat MTX levels Q 12 hrs
	10-19.9 μM	6-9.9 µM	
 
Leucovorin at 15 mg/m² at Hr 42 then continue Q 3 hours until plasma MTX is < 0.1 μM
 

			Repeat MTX levels Q 12 hrs
			Consider glucarpidase
	20-200 μM	10-100 μM	
 
Leucovorin at 100 mg/m² at Hr 42 then continue q 6 hours until plasma MTX is < 0.1 μM
 

			Repeat MTX level Q 12 hrs
			Consider glucarpidase
	>200 µM	>100 µM	
 
Leucovorin at 1000 mg/m² at hr 42 and continue q 6 hours until plasma MTX is < 0.1 μM
 

			Repeat MTX level Q 12 hrs
			Consider glucarpidase

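### Host genotype is read only from blood mononuclear cells, with no check for circulating blasts or a prior donor transplant; probably few samples are affected, and a recording and exclusion rule would cover them

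*Combined protocol and SAP*

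**What the plan says.** The target is the patient's inherited genotype. Secondary aim 1.2.2 is "To describe host polymorphisms that may identify risk of methotrexate toxicity or success of this institutional protocol", and Section 2.4 gives germline variation as the rationale: "it is known that several germline polymorphisms play a role in this variation".

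The specimen is described in Section 5.5.2: "Mononuclear cells will be separated from whole blood using Ficoll-Hypaque centrifugation", and then "DNA will be isolated from the enriched mononuclear cells". No other DNA source is named. Section 5.2 makes the tube optional and places it within 7 days before the first on-protocol dose. Section 5.5.2 explains this timing by the supply of mononuclear cells before myelosuppression, not by the purity of host DNA.

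Eligibility does not depend on disease status. Section 3.2.2 admits "Patients with any malignancy who will receive HDMTX given as a 5 g/m2 infusion over 24 hours" if a risk criterion is met. Section 4.1 adds: "Patients are eligible to be enrolled at any time point during their treatment course". Section 2 says: "Patients with relapsed ALL are at increased risk of methotrexate toxicity due to prior exposure to nephrotoxic chemotherapy". Section 5.3 records disease status and leukemia cytogenetics as descriptors only.

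Appendix A schedules "CBC with diff and platelets" at hour 0, the same column as the SNP tube. Neither the exclusion criteria nor Sections 5.2 and 5.5 or Appendix A set a remission requirement, a blast check or a rule for transplant recipients. Transplant is not mentioned anywhere.

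The genotypes are used in Section 9.1, item 2b (comparison with published minor allele frequencies) and item 2c (predictors of reaching the target concentration, with and without genotype).

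**The concern.** Leukemic blasts collect in the mononuclear fraction, so the separation step raises their share of the DNA. A clone that has lost one copy of a tested locus can make a heterozygous patient look homozygous. After an allogeneic transplant, blood cells come from the donor, and the assay reads the donor at every locus.

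In either case a genotype that is not the patient's enters analyses meant to describe how the patient handles methotrexate. Item 2b looks for departures from population frequencies in a small sample, and item 2c uses genotype as a covariate, so both are sensitive to a few wrong calls. The plan has no rule that would identify such samples.

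**Working it through.** **The plan's own figure.** The only precision statement is in Section 9.3, for the primary endpoint: 0.80 ± 1.96 × √(0.80 × 0.20/50) = 0.689 to 0.911, width 0.22. It reproduces and does not depend on genotype. The documents give no sample size or power for the SNP analyses, so everything below is illustrative.

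**Inputs.** From Section 2.4: minor allele frequencies of about 15–50%. Assumed: 30 genotyped patients, 5–20% of samples affected, and the blast shares shown.

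**Step 1: when does a blast sample mislead?** Let b be the blast share of the mononuclear cells, with blasts that have lost one allele. In a heterozygote the lost allele's share of signal is (1 − b)/(2 − b).

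| b | Share of lost allele |
|---|---|
| 80% | 0.2/1.2 = 17% |
| 50% | 0.5/1.5 = 33% |
| 40% | 0.6/1.6 = 37.5% |
| 20% | 0.8/1.8 = 44% |

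A miscall is likely at the top of this range and unlikely at the bottom. Gain of a copy does less: with 80% of cells carrying three copies, the under-represented allele still has 1.0/2.8 = 36% of the signal.

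**Step 2: how many miscalls?** Only heterozygotes are exposed, a share of 2p(1 − p): 32% at p = 0.2 and 48% at p = 0.4 (25.5% and 50% at the ends of the Section 2.4 range). If every affected clone had lost the locus and every such heterozygote were miscalled:
- low: 30 × 5% × 32% = 0.5 patients per SNP
- high: 30 × 20% × 48% = 2.9 patients per SNP

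If only 10% of the clones had lost it (assumed), these become 0.05 and 0.3. All of them scale with the number genotyped.

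**Step 3: effect on 2b from allele loss.** If either allele is equally likely to be lost, a heterozygote (one minor allele) is called with zero or two, on average one. The expected frequency does not move. The added variance is 1 per miscall. In the high case (p = 0.4, 60 alleles) the variance of the allele count goes from 60 × 0.4 × 0.6 = 14.4 to 14.4 + 2.88 = 17.28, so the standard error rises from √14.4/60 = 6.3 points to √17.28/60 = 6.9 points. A single wrong allele is 1/60 = 1.7 points.

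**Step 4: effect on 2b from donor samples.** If a share f of samples reads an unrelated donor drawn at the published frequency, the expected frequency is (1 − f) × host + f × published. Take host 30% and published 20% (assumed), with a two-sided 5% normal test on 2N alleles:

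| f | Expected frequency | Power, N = 50 | Power, N = 25 |
|---|---|---|---|
| 0 | 30% | 68% | 43% |
| 5% | 29.5% | 64% | 40% |
| 10% | 29% | 60% | 37% |
| 20% | 28% | 51% | 31% |

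The difference shrinks toward zero; no false difference is created.

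**Step 5: is early sampling needed for yield?** Section 5.5.2 expects 18.5 mcg of DNA per sample and 5–20 ng per assay: 18,500/20 = 925 to 18,500/5 = 3,700 assays. Yield is not the limiting factor, and inherited genotype does not change, so a later tube serves as well.

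**The case against.** The strongest reply is that the situation is uncommon here. Section 2.4 places high-dose methotrexate for high-risk ALL in interim maintenance, and Section 9.3 (Aim 1b) refers to interim-maintenance and similar cycles, when few blasts would be expected. Nothing describes patients with blood dominated by blasts. This stands as to size, but it is not an eligibility condition, and relapsed disease is expressly in view.

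Second, much of the information is already collected: disease status and cytogenetics in Section 5.3, a differential beside the tube in Appendix A, and batched genotyping later (Section 5.5). This also stands in part. Blast-positive samples could be flagged at analysis, but no rule says so, and transplant history is not a listed field.

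Third, the consequence is low: the tube is optional and 2b is descriptive. That is correct.

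A reader might infer more than the documents support:
- That 2 to 6 of 30 patients would be wrongly genotyped. 30 × 5–20% = 1.5 to 6 counts samples containing blasts, not miscalls.
- That blasts shift the allele frequencies of 2b in one direction. Random loss does not (Step 3).
- That relapsed patients differ in algorithm success or carry most of the information in 2c. No section says so.
- That transplant recipients are known to be enrolled. The documents are silent; they are merely not excluded.

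**Conclusion.** The gap is real and minor. Followed as written, Section 5.5.2 would put a non-host genotype into 2b and 2c for any patient sampled after a donor transplant, and could do so for a heterozygous patient with a high blast share and clonal loss at the locus. The number affected is not in the documents and is probably small. The range of 0.5 to 2.9 miscalled patients per SNP rests on 30 genotyped patients, 5–20% of samples with blasts, allele frequencies of 0.2–0.4 and certain loss of the locus; lower loss rates or blast shares bring it down. The main effect is misclassification noise from blasts and dilution from donor samples. Only optional secondary analyses are touched; the primary endpoint and its sample size are not.

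**What to change.** In Sections 5.2, 5.3 and 5.5.2:
- Record prior allogeneic transplant (yes/no) and the blast percentage from the differential drawn with the SNP tube. Section 5.2 lists only a CBC, so it should name the differential, as Appendix A does.
- In the main 2b and 2c genotype analyses, exclude samples from transplant recipients and samples with any circulating blasts. A zero threshold is the simple choice, because removing granulocytes makes the blast share of the mononuclear fraction higher than the differential shows.
- Report a sensitivity analysis that adds back the blast-positive samples, and state how many samples were excluded and why.
- Where a patient is re-enrolled for a later infusion after blasts have cleared, allow the optional tube to be drawn then instead.

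Cost: two data fields and one analysis rule, with no new assay and no change to treatment or sample size. A few samples are lost, selectively from patients with active disease or a transplant, so the genotype results would describe the remaining patients. Because tube and differential are drawn together, a replacement means a second draw of 5–10 mL, and it depends on a later on-study infusion that is not guaranteed. It should therefore stay optional.
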